Vital signs ¹⁰	X	PRE- & 15m, 30m, 1h, 2h, 4h POST-dose	PRE- & 15m, 30m, 1h, 2h, 4h POST-dose	PRE- & 15m, 30m, 1h, 2h, 4h POST-dose	X	X	X	X	X
Electrocardiogram ¹¹	X	X	X	X	X				
Hematology and biochemistry ¹²	X	X	X	X	X	X	X	X	X

	Screening ¹	DLT observation period					Continued Treatment	EoT ²	FU ³	PFS-FU ⁴	OS-FU ⁵
Week	1	3	5	6							
Day	-28 to 1	D1	D15	D29	D36						
Visit no.	Screening	C1V1	C1V2	C1V3	C1V4						
Visit window	NA	-	± 3 d	± 3 d	± 3 d						
Creatinine clearance ¹³	X										
Coagulation ¹²	X	X	X	X							
Urinalysis ¹²	X	X	X	X							
Pregnancy test ¹⁴	X	X	X	X							
PK (first 9 subjects Phase I + all subjects Arm C) ¹⁵											
Cytokines ¹⁶	X		X								
Blood sampling for immune cell phenotyping ¹⁷	X		X								
Local measurement of tumor lesion(s) ¹⁸		X	X								
Administration of CyPep-1 ¹⁹		X	X	X							
Concomitant medication ²⁰	X	X	X	X							
AEs ²¹	X	X	X	X							
iRECIST assessment ²²											
Evaluation of survival and subsequent anti- cancer therapies											X

At 8-week (±3 days) intervals while on trial treatment²³

Table 1b. Schedule of Assessments Phase I Dose Escalation and Phase IIa Arms A and C (Starting Cycle 2 and all subsequent cycles monotherapy)²⁴

Week	1	3	5	6
Day	D1	D15	D29	D36
Visit no.	Cycle X Visit 1 ²⁵ (CXV1)	CXV2	CXV3	CXV4
Visit window	± 3 d	± 3 d	± 3 d	± 3 d
Weight	X			
Physical examination	X	X	X	
Vital signs ¹⁰	PRE- & 15m, 30m, 1h, 2h, 4h POST-dose	X	X	
Tumor biopsy	X ²⁶			X ²⁶
Performance (ECOG) status ⁹	X			
Hematology and biochemistry ¹²	X			
Urinalysis ¹²	X			
Pregnancy test ¹⁴	X	X	X	
Cytokines ¹⁶			X ²⁷	
Blood sampling for immune cell phenotyping ¹⁷			X	
Local measurement of tumor lesion(s) ¹⁸	X	X	X	
Administration of CyPep-1 ¹⁹	X	X	X	
Concomitant medication ²⁰	X	X	X	X
AEs ²¹	X	X	X	X
iRECIST assessment ²²				At 8-week (+3 day/s) intervals while on trial treatment ²³

Table 1c. Schedule of Assessments Phase IIa Arm B (Cycle 1 CyPep-1 plus pembrolizumab combination)

	Screening ¹	TLT observation period			Continued Treatment	EoT ²	FU ³	PFS-FU ⁴	OS-FU ⁵
Week	1	3	5	6					
Day	-28 to 1	D1	D15	D29	D36				
Visit no.	Screening	C1V1	C1V2	C1V3	C1V4				
Visit window	NA	-	± 3 d	± 3 d	± 3 d	± 3 d	± 1 wk	± 1 wk	± 1 wk
Informed consent	X								
Demography	X								
Medical and surgical history ⁷	X								
Eligibility	X								
Tumor biopsy ⁸	X					X ²⁸			
Performance (ECOG) status ⁹	X		X	X	X	X	X		
Height ⁹	X								
Weight ⁹	X	X	X	X	X	X	X	X	
Physical examination ⁹	X	X	X	X	X	X	X	X	X

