Vital signs ¹⁰	X	PRE- & 15m, 30m, 1h, 2h, 4h POST-dose	PRE- & 15m, 30m, 1h, 2h, 4h POST-dose	PRE- & 15m, 30m, 1h, 2h, 4h POST-dose	PRE- & 15m, 30m, 1h, 2h, 4h POST-dose	X	X	X	X
Electrocardiogram ¹¹	X	X	X	X	X				
Hematology and biochemistry ¹²	X	X	X	X	X				
Creatinine clearance ¹³	X								
Coagulation ¹²	X	X	X	X	X				
Urinalysis ¹²	X	X	X	X	X			X	
Pregnancy test ¹⁴	X	X	X	X	X			X	
Cytokines ¹⁶	X					X			X

	Screening ¹	TLT observation period				Continued Treatment	EoT ²	FU ³	PFS-FU ⁴	OS-FU ⁵
Week	1	3	5	6						
Day	-28 to 1	D1	D15	D29	D36					
Visit no.	Screening	C1V1	C1V2	C1V3	C1V4					
Visit window	NA	-	± 3 d	± 3 d	± 3 d		± 3 d	± 1 wk	± 1 wk	± 1 wk
Blood sampling for immune cell phenotyping ¹⁷	X	X	X	X						
Local measurement of tumor lesion(s) ¹⁸	X	X	X	X						
Administration of CyPep-1 ¹⁹	X	X	X	X						
Administration of pembrolizumab ²⁹	X									
Thyroid function testing ³⁰	Every 6 weeks while on trial treatment									
Concomitant medication ²⁰	X	X	X	X			X	X		
AEs ²¹	X	X	X	X			X	X		
iRECIST assessment ²²						At 8-week (± 3 days) intervals while on trial treatment ²³				X
Evaluation of survival and subsequent anti-cancer therapies										X

Table 1d. Schedule of Assessments Phase IIa Arm B (Starting Cycle 2 and all subsequent cycles of CyPep-1 plus pembrolizumab combination)²³

Week	1	3	5	6
Day	D1	D15	D29	D36
Visit no.	Cycle X Visit X ²⁵ (CXV1)	CXV2	CXV3	CXV4
Visit window	± 3 d	± 3 d	± 3 d	± 3 d
Weight	X			
Physical examination	X	X	X	
Vital signs	PRE- & 15m, 30m, 1h, 2h, 4h POST-dose	X	X	
Electrocardiogram ¹¹	X			
Tumor biopsy	X ²⁶			X ²⁶
Performance (ECOG) status ⁹	X			
Hematology and biochemistry ¹²	X			
Urinalysis ¹²	X			
Pregnancy test ¹⁴	X	X	X	
Cytokines ¹⁶				X ²⁷
Blood sampling for immune cell phenotyping ¹⁷				X
Local measurement of tumor lesion(s) ¹⁸	X	X	X	
Administration of CyPep-1 ¹⁹	X	X	X	
Administration of pembrolizumab ²⁹				Every 6 weeks starting C1V1
Thyroid function testing ³⁰				Every 6 weeks while on trial treatment
Concomitant medication ²⁰	X	X	X	X
AEs ²¹	X	X	X	X
iRECIST assessment ²²				At 8-week (±3 days) intervals while on trial treatment ²³

Table 1e. Schedule of Assessments Phase IIa Arm D (CyPep-1 Monotherapy)

	Screening ¹	Treatment			Continued Weekly Treatment until Week 16	Bi-weekly Treatment	EoT ²	FU ³	PFS-FU ⁴	OS-FU ⁵
Week		1	2	3	4 to 16	17 onwards	-	-	-	-
Day	-28 to 1	D1	D8	D15	D22 to D106	D113 onwards	-	-	-	Every 3 months
Visit no.	Screening	V1	V2	V3	VN	VN'	-	-	-	-

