11. Single 12-lead ECG recordings will be taken pre-dose of CyPep-1 or pembrolizumab administration (if pembrolizumab administration day is different from CyPep-1 scheduled day). Subjects must be supine for approximately 10 minutes, before ECG collection and remain supine but awake during ECG procedure. **For Arm D:** ECG recordings will be performed both pre-dose and 30 minutes after CyPep-1 administration at screening, V1 (D1), V2 (D8), V3 (D15), and every 6 weeks from V4 (D22).
12. The safety laboratory includes hematology, biochemistry, coagulation, and urinalysis (performed by dipstick) to be performed pre-dose of CyPep-1 or pembrolizumab administration (if pembrolizumab administration day is different from CyPep-1 scheduled day). Laboratory values assessed during screening less than 72 hours before CyPep-1 administration do not need to be repeated at Visit 1. Further assessments may be performed up to 1 day prior to the visit in order to have the results (of at least Hb, WBC, platelets, PT-INR, and APTT) available on the visit day prior to CyPep-1 and/or pembrolizumab administration.
13. Creatinine clearance will be measured using CKD-EPI formula pre-dose of CyPep-1 administration or pembrolizumab administration. Assessment less than 72 hours before CyPep-1 administration do not need to be repeated at Visit 1.
14. Women of childbearing potential must have a highly sensitive negative pregnancy test at screening (serum). Pregnancy testing (highly sensitive urine/serum) should be performed before each administration of trial treatment for the duration of the trial and at EoT, with an exception for Arm D, where the frequency of pregnancy testing should be performed before each administration during the first three visits followed by every 4 weeks counting from V4 (D22), ± 3 days (see footnote 33).
15. PK assessment will be done at the following time-points: **For Phase I, and Arm C:** (up to 1 hour) pre-dose, and 15 min, 30 min, 1 hour, 2 hours, and 4 hours post-dose. **For Arm D:** (up to 1 hour) pre-dose, and 15 min, 30 min, and 1 hour post-dose. A time window of ± 5 min is allowed for the PK blood samples.

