24. Continuous Q2W CyPep-1 treatment is planned and until confirmed PD, unacceptable toxicity or consent withdrawal, loss to follow up, or trial end, whichever occurs first. Lesions not originally planned to be injected with CyPep-1 at screening may also be injected per investigator's discretion, if necessary and after consulting with medical monitor. Follow-up visits will follow the interval as defined in **Table 1a/c**. For subjects in the combination arm treatment with pembrolizumab will continue as per SoC following Q6W dosing until PD, unacceptable toxicity or consent withdrawal.

25. Per additional cycles: C2, C3, ...Cn. CXV1 is scheduled 2 weeks after the last CyPep-1 administration (to follow a Q2W administration schedule).

26. If a subject is receiving additional Q2W treatment with CyPep-1, a biopsy of any new injected lesion(s) can be taken (not mandatory) after 6 weeks for each subsequent cycle. A biopsy at CxD1 (pre-dose) is only applicable if any new lesion(s) are selected for CyPep-1 injection (not mandatory). Arrangements to be made for any tumor material to be sent for analysis are described in the laboratory manual. The visit window for biopsies on CxV4 is ± 3 days.

27. Cytokine levels should only be assessed in the first and second cycles of CyPep-1 administration.

28. The visit window for biopsies on C1V4 is ± 3 days.

29. Pembrolizumab administration only in the combination arm (Arm B). Pembrolizumab should be administered as per SOC Q6W independent of other administrations or assessments (see **Section 5.3.2** for details regarding pembrolizumab administration). CyPep-1 should be administered 30 to 60 min after pembrolizumab if on the same day. All safety assessments and safety laboratory testing should be performed on all pembrolizumab administration days as specified in **Table 1c**. Pembrolizumab will be administered using IV infusion after all procedures and assessments have been completed. See **Section 5.3.6.2** for dose modifications and toxicity management. Pembrolizumab will be administered to a maximum of 18 cycles and then stopped.

30. Thyroid panel should include: triiodothyronine (T3) or free triiodothyronine (FT3); free thyroxine (FT4); thyroid stimulating hormone (TSH).

31. The frequency for tumor biopsy is every 6 weeks from D1 if a subject stays on treatment. The biopsy of at least one injected lesion is highly desired but not mandatory.

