32. Frequency of assessments is every 6 weeks counting from V4 ([D22], ± 3 days).

33. Frequency of assessments is every 4 weeks counting from V4 ([D22], ± 3 days).

34. A lesion map that will guide the preferred sequence of injection of the identified Lesion Sets must be created prior to the first CyPep-1 injection (detailed in **Study Procedural Manual**). The lesion map should be updated at every visit during the treatment period. Once all injectable lesions have been injected and the subject remains on treatment, a new lesion map permits

reprioritizing of the to-be-injected Lesion Sets will be created, taking into account size changes of individual lesions, e.g., an individual lesion enlarged or regressed after initial 3 doses of CyPep-1 injections. For details see [Section 5.3.1.3](#).

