Parameters to be assessed include: hemoglobin, hematocrit, RBC count, WBC count with differential count (neutrophils, eosinophils, basophils, lymphocytes, monocytes), and platelet count. Further assessments may be performed up to one day prior to the visit in order to have the results (of at least hemoglobin, white blood cells, platelets, PT-INR, and APTT) available on the visit day prior to CyPep-1 administration.

The Investigator (or qualified designee) should evaluate all blood parameters either as normal or abnormal. If an abnormal finding is encountered, the investigator should indicate whether the finding is clinically significant or not. Any hematological abnormalities that are considered to be clinically significant need to be followed until resolution.

Biochemistry

At the time points indicated in [Table 1](#), blood sampling for all safety laboratory tests should be performed and results should be available prior to administration of CyPep-1 or pembrolizumab (if pembrolizumab administration day is different from CyPep-1 scheduled day).

Biochemistry tests will be performed at the local (institute's) hospital.

Parameters to be assessed include: creatinine, total bilirubin, direct bilirubin (only applicable if total bilirubin levels > 1.5 x ULN), alkaline phosphatase, phosphate, ALAT, ASAT, GGT, total protein, albumin, uric acid, urea, sodium, potassium, calcium, chloride, glucose, LDH, amylase and lipase. Creatinine clearance will be estimated according to the CKD-EPI formula.

The Investigator (or qualified designee) should evaluate all clinical chemistry parameters either as normal or abnormal. If an abnormal finding is encountered, the Investigator should indicate whether the finding is clinically significant or not. Any clinical chemistry abnormalities that are considered to be clinically significant need to be followed until resolution.

Coagulation

Coagulation parameters will be assessed at several different time points throughout the trial (Table 1) and include PT-INR-, and activated partial thromboplastin time (APPT) prior to dosing. In case there are no normal ranges available for the PT test, the international normalized ratio (INR) test may be used instead of PT. At screening, subjects should have an INR <1.5 x ULN.

Urinalysis

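### Tables 1b and 1d carry no coagulation row from Cycle 2: in Arm B this contradicts footnote 29, and in Arms A and C injections continue with no scheduled PT-INR/APTT after Cycle 1

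*Protocol*

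**What the plan says.** Three of the five schedule tables have a separate coagulation row: Table 1a (Phase I, Arms A and C, Cycle 1), Table 1c (Arm B, Cycle 1) and Table 1e (Arm D). Tables 1b and 1d, which cover Cycle 2 onwards for the same arms as 1a and 1c, have none. Their laboratory rows are hematology/biochemistry and urinalysis (both with footnote 12, both marked at CXV1) and the pregnancy test. CyPep-1 is marked at CXV1, CXV2 and CXV3.

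The relevant footnotes and text are:

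- Footnote 12, on content: "The safety laboratory includes hematology, biochemistry, coagulation, and urinalysis (performed by dipstick) to be performed pre-dose of CyPep-1 or pembrolizumab administration".
- Footnote 29, on the pembrolizumab row of Table 1d: "All safety assessments and safety laboratory testing should be performed on all pembrolizumab administration days as specified in" Table 1c.
- Footnote 19, for weekly dosing in Cycle 1 (lesions above 7 cm): coagulation is listed among the additional assessments on Day 36.
- Footnote 32, on the Arm D coagulation row: "Frequency of assessments is every 6 weeks counting from V4".
- Protocol 6.2, Coagulation, places the test at several "time points throughout the trial (Table 1) and include PT-INR-, and activated partial thromboplastin time (APPT) prior to dosing". It therefore points back to the tables.

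SAP 11.4 also leaves laboratory timing to the Schedule of Assessments.

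**The concern.** CyPep-1 is given by needle into tumor tissue, in Arm C under ultrasound guidance into a liver metastasis (Protocol 5.3.1), and treatment is open-ended. Exclusion criterion 10 admits anticoagulated subjects to Arms A and C if their values lie in the therapeutic interval, and it is checked at screening. A coagulation result is the obvious pre-injection check for such subjects, yet the tables drop it once Cycle 1 ends.

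The protocol elsewhere links this test to injections. It is marked at Cycle 1 injection visits, added on Day 36 when an injection is added, and kept every 6 weeks in Arm D, where metastatic disease is limited to skin, subcutaneous, nodal and lung sites. No reason is given for omitting it in Arm C after Cycle 1.

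Two things are at stake. One is an avoidable gap in scheduled safety testing before liver and other injections. The other is uneven data: SAP 11.4 summarizes coagulation by visit and as shifts to worst grade, and after Cycle 1 those outputs would depend on which sites chose to test.

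**Working it through.** **Row check for coagulation.** Table 1a present; 1b absent; 1c present; 1d absent; 1e present, 6-weekly from V4. Tables 1b and 1d both run to their last row (iRECIST) and lack the same row, so loss in text extraction is unlikely, though it cannot be excluded.

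**Arm B.** Pembrolizumab is given on Day 1 of each 6-week cycle (Protocol 5.3.2). Footnote 29 requires the Table 1c safety laboratory on each of those days, and Table 1c includes coagulation. Table 1d does not show it. Footnote and table therefore contradict each other, and the footnote is the explicit instruction.

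**Arms A and C: does footnote 12 schedule the test?** The hematology/biochemistry row of Table 1a carries footnote 12 and appears to be marked on Day 36 as well. If footnote 12 brought coagulation along with that row, footnote 19 would not need to add coagulation on Day 36. It does add it. The rows therefore set the timing and footnote 12 states what the laboratory panel is.

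**Age of the latest scheduled PT-INR/APTT in Arms A and C.** Visit days come from SAP Appendix 4, Table 10. The last scheduled test by the rows of Table 1a is Day 29. Age = injection day − 29.

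| Cycle | D1 | D15 | D29 |
|---|---|---|---|
| 2 | 43 − 29 = 14 | 57 − 29 = 28 | 71 − 29 = 42 |
| 3 | 85 − 29 = 56 | 99 − 29 = 70 | 113 − 29 = 84 |
| 6 | 211 − 29 = 182 | 225 − 29 = 196 | 239 − 29 = 210 |

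With weekly Cycle 1 dosing and a Day 36 test, the D29 ages on the same visit days are 71 − 36 = 35, 113 − 36 = 77 and 239 − 36 = 203 days.

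**With a test at CXV1.** Ages at D1, D15 and D29 are 0, 15 − 1 = 14 and 29 − 1 = 28 days in every cycle. The oldest result falls from 42 to 28 days in Cycle 2, from 84 to 28 in Cycle 3 and from 210 to 28 in Cycle 6.

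**Comparison with Arm D.** The scheduled interval there is 6 × 7 = 42 days. In Cycle 2 the oldest result in Arms A and C equals that interval; from Cycle 3 D1 (56 days) it exceeds it.

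All days are nominal and ignore the ±3-day visit windows. Treatment duration is not stated, so Cycles 2, 3 and 6 are illustrations.

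**The case against.** The best defense is that the omission is deliberate. Table 1b also drops ECG and creatinine clearance, and vital signs are reduced on later treatment days once the observation period for dose-limiting toxicity is over. Arm D is an imperfect benchmark: it doses weekly to week 16, spreads injections over as many lesions as possible, and has no formal DLT period. Other protection exists:

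- The synopsis and SAP Section 11 allow additional assessments when clinically indicated.
- Protocol 5.6.1 has anticoagulants stopped at the investigator's discretion and by local practice.
- Exclusion 11 concerns stop-start anticoagulation.
- Inclusion 6 and exclusions 21 and 22 limit bleeding risk, liver involvement and vessel invasion in Arm C.
- Platelets and liver biochemistry continue at CXV1.
- The Study Procedural Manual, not among the documents, may add checks.

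Most of this stands. It means the gap is one in scheduled testing and does not show that any subject goes untested. It does not explain Arm B, where footnote 29 is explicit, or why the test is added for an extra injection on Day 36 and then dropped for all later injections.

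A reader might go further and infer that footnote 12 itself requires PT-INR/APTT at CXV1 in Arms A and C, so that Table 1b contradicts it. The documents do not support that. Footnote 19 shows that coagulation has to be added separately. The clause naming the results "of at least Hb, WBC, platelets, PT-INR, and APTT) available on the visit day prior to CyPep-1 and/or pembrolizumab administration" belongs to a sentence saying that assessments may be done up to a day early; it is a permissive window, and the similar sentence in Protocol 6.2 reads the same way. Taken literally, footnote 12 would also demand laboratory tests before the CXV2 and CXV3 doses, where none are marked.

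**Conclusion.** The point holds in two parts of different weight. In Arm B, Table 1d contradicts footnote 29. This is a real inconsistency, but the footnote already requires the test on every pembrolizumab day, so the correction is editorial. In Arms A and C the plan as written schedules no PT-INR/APTT at treatment visits after Cycle 1 Day 29 (Day 36 with weekly dosing), while injections go on every 2 weeks. The latest scheduled result at the D29 injection is then 42, 84 and 210 days old in Cycles 2, 3 and 6.

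For Arms A and C this is out of step with the protocol's own practice and worth correcting, but it is not a proven error. A reader might infer a demonstrated bleeding hazard; the documents give no bleeding rate, no share of anticoagulated subjects and no sign that CyPep-1 alters coagulation, so the clinical risk is unquantified. The conclusion assumes that the rows govern timing, that Tables 1b and 1d are complete as read, and that SAP Table 10 visit days apply. Sample size and the efficacy analyses are unaffected.

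**What to change.** Add a pre-dose coagulation row (PT-INR, APTT) at CXV1 to Tables 1b and 1d, drawn with the D1 hematology and biochemistry sample. This aligns Table 1d with footnote 29 and gives Arms A and C the same 6-weekly interval as Arm D.

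The cost is a protocol amendment to two tables, with no extra visit or blood draw. In Arms A and C it adds one assay per subject per 6-week cycle: at most 18 + 9 = 27 per cycle if Arm A is fully expanded and everyone continues, and fewer where sites already test at that visit. In Arm B it adds nothing on pembrolizumab days. Phase I, also under Table 1b, has completed dose escalation. The limitation is that D15 and D29 injections would still rely on a result 14 to 28 days old.

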16. XXXXXXXXXX
17. Peripheral blood phenotyping of selected immune cell markers will be performed by a central laboratory.
18. **For Phase I, and Phase IIa Arms A, B, and D:** Local measurements of accessible (to-be) injected cutaneous/subcutaneous tumor lesion(s) must be done within one day (<24 h) prior to each CyPep-1 injection by caliper and color digital photography, using a ruler held flush to the skin next to the longest diameter of the lesion to indicate the size of the lesion. If needed, guidance with ultrasound is permitted. The (to-be) injected lesions under ultrasound control must be measured with ultrasound guidance before each CyPep-1 injection and only on dates of CyPep-1 injection. All ultrasound and color digital photography, image files should be stored and available in the patient file. Lesion(s) that disappeared will be checked on the days of CyPep-1 injections. **For Arm C:** If lesion injections are performed under CT-guidance, the volume measurement will be performed by CT **For Arm D:** Lesions identified as non-injected lesions will be measured following the procedures as the (to-be) injected lesions above in a 4-week interval starting at D1. Details on local measurement to determine the injection volume see [Section 5.3.1.3](#).
19. Premedication is mandatory prior to the first IT dose of CyPep-1. Premedication is started 30-60 minutes before the IT injection, and continues for up to 24-48 hours after the procedure was completed, if necessary. An antihistamine (e.g., 25 to 50 mg clemastine) is mandatory with optional anxiolytics if deemed appropriate by the investigator. Only for subjects experience pain

during or after IT administration, it is recommended to provide celecoxib 400 mg as premedication every 6 hours for 24-48 hours. Premedication should be administered for subsequent CyPep-1 doses based upon clinical judgment and presence/severity of prior reactions. This regimen may be modified based on local treatment standards and guidelines as appropriate. To ensure prophylactic hydration, subjects should consume ≥ 2 L of fluid intake per day, starting ≥ 48 hours prior to first dose/each dose escalation and for ≥ 24 hours thereafter. For subjects who have difficulty to maintain adequate oral hydration, intravenous hydration is recommended, at an infusion rate of 150-200 mL/hr (i.e., $2\text{-}3$ L per day) for initial dosing; for following dose escalations, an intravenous hydration with 1.5-2 L per day is advisable. For lesions > 7 cm, weekly CyPep-1 administration should be considered by the Investigator for the first 6 weeks, on Days 1, 8, 15, 22, 29 and 36 of cycle 1. The assessments are as per scheduled visit for Day 1, 15 and 29. Visits on Day 8 and 22 will follow the assessments as per D15 (C1V2) with the exclusion of central lab sampling for cytokine analysis and blood sampling for immune cell phenotyping. For Day 36 assessments as specified in the schedule need to be performed, with additional assessments: Pre-dose ECG, Vital Signs PRE- & 15m, 30m, 1h, 2h, 4h POST-dose, Coagulation and Pregnancy test (if applicable).

20. All concomitant medication/procedures should be reported beginning upon ICF signature until FU (or EoT, if it occurs more than 30 days after the last CyPep-1 or pembrolizumab administration).

21. Reporting period is from ICF signature until FU (or EoT, if it occurs more than 30 days after the last CyPep-1 or pembrolizumab administration). After the FU visit (or EoT, if it occurs more than 30 days after the last CyPep-1 or pembrolizumab administration), only ongoing (S)AEs related to CyPep-1 or pembrolizumab administration will be collected. Adverse events will be assessed using CTCAE v5.0 including start and stop dates, severity, relationship to CyPep-1 or pembrolizumab, outcome and action taken.

22. Radiological assessment should include chest, abdomen, pelvis and all other known sites of disease. The baseline scan for radiological assessment is to be done within 4 weeks prior to C1V1 (V1 for Arm D). If radiological assessments has been done in clinical routine within 4 week before Visit 1 and scan fulfills requirements for iRECIST (and additionally iiRECIST for Arm D) evaluation, this scan can be used for baseline evaluation (not need to be repeated during screening). Follow-up scans are to be performed every 8 weeks starting C1V1 (V1 for Arm D). The window for follow up radiological assessments during the trial is ± 3 days. Once a tumor lesion(s) is documented, the target area should be recorded at every subsequent time-point for the duration of the trial. Efficacy assessment will be based on RECIST (and additionally iiRECIST for Arm D) for up to 10 target lesions. All skin lesions must be assessed by caliper measurement during clinical exam on the dates corresponding to iRECIST/iiRECIST assessment. Documentation by color photography including a ruler to estimate the size of the lesion should be stored in the patient file.

23. A confirmatory radiological assessment only has to be done if PD was observed with the previous radiological assessment. If the lesion(s) continue(s) to enlarge, the original PD will be considered as the 'first documented PD'. If lesion(s) remain(s) unchanged or decrease(s) in size, assessments should continue as per protocol (i.e., the next radiological assessment will be performed after an 8-week interval). In this case, the first measured PD will be disregarded. In case of unconfirmed PD after the first (or subsequent) cycle, the subject may continue Q2W administrations of CyPep-1 and Q6W administrations of pembrolizumab in the combination arm. If PD is confirmed 4 weeks later, then the subject will be taken off-trial and move to the EoT visit.

24. Continuous Q2W CyPep-1 treatment is planned and until confirmed PD, unacceptable toxicity or consent withdrawal, loss to follow up, or trial end, whichever occurs first. Lesions not originally planned to be injected with CyPep-1 at screening may also be injected per investigator's discretion, if necessary and after consulting with medical monitor. Follow-up visits will follow the interval as defined in **Table 1a/c**. For subjects in the combination arm treatment with pembrolizumab will continue as per SoC following Q6W dosing until PD, unacceptable toxicity or consent withdrawal.

25. Per additional cycles: C2, C3, ...Cn. CXV1 is scheduled 2 weeks after the last CyPep-1 administration (to follow a Q2W administration schedule).

26. If a subject is receiving additional Q2W treatment with CyPep-1, a biopsy of any new injected lesion(s) can be taken (not mandatory) after 6 weeks for each subsequent cycle. A biopsy at CxD1 (pre-dose) is only applicable if any new lesion(s) are selected for CyPep-1 injection (not mandatory). Arrangements to be made for any tumor material to be sent for analysis are described in the laboratory manual. The visit window for biopsies on CxV4 is ± 3 days.

27. Cytokine levels should only be assessed in the first and second cycles of CyPep-1 administration.

28. The visit window for biopsies on C1V4 is ± 3 days.

29. Pembrolizumab administration only in the combination arm (Arm B). Pembrolizumab should be administered as per SOC Q6W independent of other administrations or assessments (see **Section 5.3.2** for details regarding pembrolizumab administration). CyPep-1 should be administered 30 to 60 min after pembrolizumab if on the same day. All safety assessments and safety laboratory testing should be performed on all pembrolizumab administration days as specified in **Table 1c**. Pembrolizumab will be administered using IV infusion after all procedures and assessments have been completed. See **Section 5.3.6.2** for dose modifications and toxicity management. Pembrolizumab will be administered to a maximum of 18 cycles and then stopped.

30. Thyroid panel should include: triiodothyronine (T3) or free triiodothyronine (FT3); free thyroxine (FT4); thyroid stimulating hormone (TSH).

31. The frequency for tumor biopsy is every 6 weeks from D1 if a subject stays on treatment. The biopsy of at least one injected lesion is highly desired but not mandatory.

32. Frequency of assessments is every 6 weeks counting from V4 ([D22], ± 3 days).

33. Frequency of assessments is every 4 weeks counting from V4 ([D22], ± 3 days).

34. A lesion map that will guide the preferred sequence of injection of the identified Lesion Sets must be created prior to the first CyPep-1 injection (detailed in **Study Procedural Manual**). The lesion map should be updated at every visit during the treatment period. Once all injectable lesions have been injected and the subject remains on treatment, a new lesion map permits

reprioritizing of the to-be-injected Lesion Sets will be created, taking into account size changes of individual lesions, e.g., an individual lesion enlarged or regressed after initial 3 doses of CyPep-1 injections. For details see [Section 5.3.1.3](#).

